- v) Concurrent chemotherapy administered with primary radiation and adjuvant chemotherapy given following completion of radiation therapy do not count as systemic therapies, though participants who progressed less than 6 months from primary platinum-based therapy are eligible.
- vi) Participants must have been offered and/or have received or refused at least 1 prior approved immune therapy regimen, that is considered standard of care for their disease stage and condition, in the country where they are receiving treatment, if such a regimen exists. Reason(s) for refusal should be documented.
- g) MEL
 - i) Participants must have histologically confirmed recurrent or metastatic melanoma not amenable to local therapy with curative intent (surgery with or without chemotherapy)
 - ii) Participants must have known BRAF and NRAS mutation status.
 - iii) Participants must have received and progressed/been intolerant of at least 1 but no more than 3 prior systemic therapies for metastatic and/or unresectable disease and have been considered for all other potentially efficacious therapies.
 - iv) Participants must have been offered and/or have received or refused at least 1 prior approved immune therapy regimen, that is considered standard of care for their disease stage and condition, in the country where they are receiving treatment, if such a regimen exists. Reason(s) for refusal should be documented.

h) RCC

- i) Participants must have histologically confirmed advanced or metastatic RCC with a clear cell component, not amenable to curative surgery.
- ii) Must have received at least 1 but not more than 3 prior systemic therapies in the advanced or metastatic setting. Systemic therapies may include anti-angiogenic therapy regimens (including but not limited to sunitinib, sorafenib, pazopanib, axitinib, tivozanib, and bevacizumab), cytokine therapy (eg, IL-2, IFN- α), vaccine therapy, or treatment with cytotoxics.

- iii) Participants must have evidence of progression on or after the last treatment regimen received and within 6 months prior to study enrollment.
- iv) Participants must have been offered and/or have received or refused at least 1 prior approved immune therapy regimen, that is considered standard of care for their disease stage and condition, in the country where they are receiving treatment, if such a regimen exists. Reason(s) for refusal should be documented.

i) TNBC

- i) Participants must be women with histologically or cytologically confirmed breast carcinoma.
- ii) Tumor must be "triple receptor negative" defined as ER/progesterone negative per local lab and HER-2 negative defined as HER-2 0 or 1+ by IHC, or IHC 2+ and ISH not amplified, or ISH-non amplified.
- iii) Participants must have progression or refractory disease.
- iv) Participants must have had at least 1 and not more than 3 systemic chemotherapeutic, targeted or investigational regimens for the treatment of metastatic or locally advanced and unresectable disease.
- v) Participants may refuse chemotherapy for their disease. Participants actively refusing chemotherapy must have had best response of stable disease, or progression or refractory disease to other treatment options such as radiotherapy, targeted agents, or investigational therapy prior to starting study treatment. The participant's refusal must be thoroughly documented. The investigator will discuss each individual participant refusing chemotherapy with the sponsor's Medical Monitor/Study Director (or designee) to confirm eligibility.
- vi) Participants must have been offered and/or have received or refused at least 1 prior approved immune therapy regimen, that is considered standard of care for their disease stage and condition, in the country where they are receiving treatment, if such a regimen exists. Reason(s) for refusal should be documented.

4) Physical and laboratory test findings

- a) Adequate hematologic function
 - i) White blood cells $\geq 2,000/\mu L$
 - ii) Neutrophils \geq 1,500/µL (stable off any growth factor within 4 weeks of first study treatment administration)
 - iii) Platelets $\ge 100 \times 10^3 / \mu L$ (transfusion to achieve this level is not permitted within 2 weeks of first study treatment administration)
 - iv) Hemoglobin ≥ 9.0 g/dL (transfusion to achieve this level is not permitted within 2 weeks of first study treatment administration)
- b) Adequate hepatic function
 - i) ALT and AST $\leq 3 \times$ upper limit of normal (ULN)
 - ii) Total bilirubin ≤ 1.5× ULN (except participants with Gilbert's syndrome who must have normal direct bilirubin)
- c) Normal thyroid function or stable on hormone supplementation per investigator assessment

Revised Protocol No.: 04 Date: 31-May-2019 d) Serum creatinine $\leq 1.5 \times$ ULN or creatinine clearance (CrCl) ≥ 40 mL/min (measured using the Cockcroft Gault formula below):

Female CrCl = $(140 - age in years) \times weight in kg \times 0.85$

 $72 \times \text{serum creatinine in mg/dL}$

Male $CrCl = (140 - age in years) \times weight in kg \times 1.00$

 $72 \times \text{serum creatinine in mg/dL}$

- e) Ability to comply with treatment, PK and PD sample collection, and required study followup.
- f) Participant re-enrollment: This study permits the re-enrollment of a participant who has discontinued the study as a pretreatment failure (eg, participant has not been treated). If re-enrolled, the participant must be re-consented.

5) Age and Reproductive Status

- a) Males and females, ages ≥ 18 years at the time of informed consent.
- b) Women of childbearing potential (WOCBP) must have a negative serum or urine pregnancy test (minimum sensitivity of 25 IU/L or equivalent units of human chorionic gonadotropin) within 24 hours prior to the start of study treatment.
- c) Women must not be breastfeeding.
- d) WOCBP must agree to follow instructions for method(s) of contraception for the duration of study treatment with nivolumab or ipilimumab and 5 months after the last dose of study treatment (ie, 30 days [duration of ovulatory cycle] plus the time required for the investigational drug to undergo approximately 5 half-lives).
- e) Males who are sexually active with WOCBP must agree to follow instructions for method(s) of contraception for the duration of study treatment with nivolumab or ipilimumab and 7 months after the last dose of study treatment (ie, 90 days [duration of sperm turnover] plus the time required for the investigational drug to undergo approximately five half-lives). In addition, male participants must be willing to refrain from sperm donation during this time.
- f) Due to potential presence of study drugs in seminal fluid, azoospermic males who are sexually active must use condoms for all sexual activity during study treatment. Additionally, condoms must continue to be used for 4 months after the participants' final treatment. WOCBP who are continuously not heterosexually active are also exempt from contraceptive requirements, and still must undergo pregnancy testing as described in this section.

Investigators shall counsel WOCBP and male participants who are sexually active with WOCBP on the importance of pregnancy prevention and the implications of an unexpected pregnancy. Investigators shall advise on the use of highly effective methods of contraception (see Appendix 4), which have a failure rate of < 1% when used consistently and correctly.

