 - v) Participants with known EGFR mutations or ALK rearrangements must have received EGFR or ALK inhibitors, respectively. EGFR, ALK, KRAS, and ROS1 mutational status must be documented, if known.

Revised Protocol No.: 04 Date: 31-May-2019

- vi) Participants must have been offered and/or have received or refused at least 1 prior approved immune therapy regimen, that is considered standard of care for their disease stage and condition, in the country where they are receiving treatment, if such a regimen exists. Reason(s) for refusal should be documented.
- vii) Participants must have had at least 1, but not more than 3 prior systemic therapies for NSCLC. Maintenance, adjuvant, or neoadjuvant (chemotherapy or chemoradiation) therapy do not count as an additional line of treatment.

d) PRC

- i) Participants must have histologic or cytologic confirmation of adenocarcinoma of the prostate.
- ii) "Not applicable as per revised protocol 02" Participants have been treated by orchiectomy or are receiving a luteinizing hormone-releasing hormone analog, and have a testosterone level \leq 50 ng/dL.
- iii) "*Not applicable as per revised protocol 02*" Metastatic disease by any 1 of the following modalities: computerized tomography (CT), magnetic resonance imaging (MRI), and bone scan.
 - a. Participants with bone-only disease should have progression confirmed as per PCWG3 criteria and require confirmatory scans.
- iv) Participants must have received abiraterone or enzalutamide.
- v) *"Not applicable as per revised protocol 02"* Progression during hormonal treatment. For eligibility purposes, progressive disease is defined as:
 - (1). Rising prostate-specific antigen values at a minimum of 1-week intervals and a 2.0-ng/mL minimum starting value OR;
 - (2). Progression per bone scan: the appearance of 2 or more new lesions, OR;
 - (3).Progression per target lesions/measurable disease: nodal progression, per modified RECIST v1.1. Only lymph nodes > 2 cm will be considered to assess a change in size qualifying for disease progression.
- vi) Anti-androgens (bicalutamide, flutamide, nilutamide) or adrenal androgen production inhibitors (aminoglutethamide or ketoconazole) should be discontinued 28 days prior to starting study treatment. Note: bicalutamide or nilutamide must be discontinued within 6 weeks of study arm assignment.

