 - (1). Participants with a history of response to an anti-androgen or adrenal androgen production inhibitor and subsequent progression while on that anti-androgen should be assessed for anti-androgen withdrawal response for 4 weeks, and must demonstrate progression.
 - (2). For participants who have never responded to anti-androgens, observation for antiandrogen withdrawal response is not necessary; however, a 2-week washout period is required prior to start of study treatment.
- vii) Evidence of M1 metastatic disease on previous bone, CT, and/or MRI scan.
 - viii) Ongoing ADT with a gonadotropin-releasing hormone (GnRH) analogue or bilateral orchiectomy (ie, surgical or medical castration) confirmed by testosterone levels of 1.73 nmol/L (≤ 50 ng/dL) at the screening visit. Castrate levels of testosterone must be maintained by surgical or medical means (leuteinizing

hormone-releasing hormone (LHRH / GnRH analogues) throughout the conduct of the study.

- ix) Documented prostate cancer progression as per PCWG3 criteria³⁹ (see Appendix 11) with one of the following:
 - (1).PSA progression* defined by a minimum of 2 rising PSA levels with an interval of ≥ 1 week between each determination with either (a) soft tissue disease progression or (b) bone disease progression or both (a) and (b). The PSA value at the screening visit should be $\geq 2\mu g/L$ (2 ng/mL).
 - (2). Soft tissue disease progression defined by RECIST v1.1. Participants whose disease spread is limited to regional pelvic lymph nodes will be considered eligible.
 - (3).Bone disease progression with 2 or more new lesions on bone scan.

*Participants who received an anti-androgen must have progression after withdrawal (≥ 4 weeks since last flutamide administration or ≥ 6 weeks since last bicalutamide or nilutamide administration)

- x) Participants with bone-only disease may not be eligible if a soft tissue fresh pretreatment and on-treatment tumor biopsies cannot be provided.
- xi) "*Not applicable as per revised protocol 03*" Participants must have received 1 but not more than 2 prior regimens for castration-resistant disease. If docetaxel chemotherapy is used more than once, this will be considered as one regimen.
- xii) Participants must have received 1 but not more than 3 prior regimens for castrationresistant disease. If docetaxel chemotherapy is used more than once, this will be considered as one regimen.

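### Prostate criterion vi Note: the six-week bicalutamide/nilutamide limit is worded as a maximum, where the footnote to criterion ix sets a minimum

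*Combined protocol and SAP*

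**What the plan says.** All the text at issue is in protocol section 6.1, 3) d) PRC.

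- Criterion vi, main sentence: anti-androgens and adrenal androgen production inhibitors "should be discontinued 28 days prior to starting study treatment". This is a minimum with no upper limit.
- Criterion vi, Note: "Note: bicalutamide or nilutamide must be discontinued within 6 weeks of study arm assignment".
- Criterion vi(2), for men who have never responded to anti-androgens: "observation for antiandrogen withdrawal response is not necessary", but "a 2-week washout period is required prior to start of study treatment".
- Criterion ix, footnote: "Participants who received an anti-androgen must have progression after withdrawal". The parenthesis that follows sets at least 4 weeks for flutamide and, for the two drugs in the Note, "≥ 6 weeks since last bicalutamide or nilutamide administration". The asterisk appears only on route ix(1), "PSA progression* defined by a minimum of 2 rising PSA levels". Routes ix(2), soft tissue progression, and ix(3), bone progression, carry none.

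These items are current. Criteria ii, iii, v and xi in the same list are marked as no longer applicable; vi and ix are not. Section 6 requires every criterion to be met before Day 1 dosing and rules out exceptions, and section 9 disallows waivers.

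**The concern.** The Note and the footnote use the same number for the same two drugs in opposite directions. The Note sits in a washout criterion, where a minimum is expected, but its wording sets a ceiling.

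Eligibility is at stake. A site that applies the Note as printed turns away men who have been off bicalutamide or nilutamide longer than the footnote asks. A site that reads the Note as a minimum enrols the same men. Because exceptions and waivers are barred, a site has no sanctioned way to settle the matter by judgement, and a man enrolled at eight weeks off drug is, on the printed words, an eligibility deviation.

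**Working it through.** The plan states no figure to reproduce. The check is which gaps from last dose to arm assignment each rule allows.

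**Inputs**
- G = days from last bicalutamide or nilutamide dose to arm assignment.
- h = days from arm assignment to first dose. The documents do not give h. Table 2-1 places treatment assignment after all screening procedures are complete, and the tetanus booster at Day -7 to -3, so h = 0, 3 and 7 are taken as assumptions.
- 6 weeks = 42 days.

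**Rules**
- 28-day rule (vi): G + h ≥ 28.
- Note as printed: G ≤ 42.
- Footnote interval (ix): at least 42 days off drug, with progression after withdrawal. The footnote names no date to count to, so two versions are tried: progression shown by assignment (G ≥ 42), or by first dose (G + h ≥ 42).

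**Values of G that satisfy the rules with the Note as printed**

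| h | Note + 28-day rule | adding footnote, by assignment | adding footnote, by first dose |
|---|---|---|---|
| 0 | 28 to 42 | 42 only | 42 only |
| 3 | 25 to 42 | 42 only | 39 to 42 |
| 7 | 21 to 42 | 42 only | 35 to 42 |

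No column admits G above 42. For example, 8 weeks is 56 days. A man at G = 56 satisfies the 28-day rule and the footnote's interval but exceeds the Note by 56 − 42 = 14 days.

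**With the Note read as a minimum (G ≥ 42)**

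G + h is then also at least 42, which exceeds 28. The 28-day rule and the footnote's interval hold under either counting date, for every G from 42 upward and for any h. The conflict disappears without moving the Note's reference point away from arm assignment.

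**The case against.** The best defence is that no sensible site would apply a ceiling. The Note follows directly on a correctly worded minimum, sits above two further washout items, and has a counterpart in the footnote that gives the same threshold as a minimum. This is persuasive about intent, and it is why the Note is very probably a slip. It does not make the printed criterion correct, and the criteria are declared binding without exception.

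A reader might also infer more than the text supports:

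- **That almost nobody could qualify.** The single-day window arises only where the footnote applies and only for some counting dates. If the asterisk is taken as printed, the footnote attaches to ix(1) alone. That route already requires soft tissue or bone progression, so a man who meets it will usually also meet an unstarred route. Without the footnote, the printed Note and the 28-day rule leave 28 to 42 days at h = 0.
- **That men with earlier chemotherapy are systematically shut out.** Criterion iv says "Participants must have received abiraterone or enzalutamide", and criterion xii asks for one to three regimens for castration-resistant disease. Neither requires bicalutamide, nilutamide or a cytotoxic agent, so the number affected cannot be derived.
- **That vi(2) contradicts the footnote.** vi(2) is nested under vi and states its own washout, so reading it as a specific exception is natural. It waives observation for a withdrawal response, whereas the footnote requires progression after withdrawal. These are related but not identical. Its status, like the reach of the asterisk, needs clarifying; neither is shown to be an error.
- **That efficacy or safety results are affected.** The documents give no count of prostate participants or of men with prior bicalutamide or nilutamide.

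**Conclusion.** The point holds in a limited form. The Note's wording sets a maximum where a minimum was almost certainly meant. Read literally, it excludes men more than 42 days off bicalutamide or nilutamide who meet the footnote. That exclusion follows from the Note alone and does not depend on h. The conflict with the footnote is direct only where the footnote applies, and the exact overlap depends on a counting date that the footnote does not give. Severity is minor: it is a wording correction to one threshold in one of nine named tumour types.

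**What to change.** Reword the Note in criterion vi to: _bicalutamide or nilutamide must be discontinued at least 6 weeks before study arm assignment_. Keep arm assignment as the reference point.

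The cost falls on men not already held to six weeks by the footnote. Those who would have been assigned at 28 to 41 days off drug wait 1 to 14 days more (42 − 41 to 42 − 28). If assignment precedes first dose by h days, the earliest first dose moves from Day 28 to Day 42 + h, a delay of 14 + h days: 17 at h = 3 and 21 at h = 7.

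In the same edit the sponsor may also state two things:

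- Whether vi(2) is an exception for never-responders. Their minimum before first dose is 14 days if it is. If it is not, it is 28 days under the general rule, and for bicalutamide or nilutamide at least 42 days under the reworded Note. For those two drugs that is at least 42 − 14 = 28 days later than vi(2) allows.
- Whether the footnote covers ix(2) and ix(3) as well as ix(1).

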6.2 Exclusion Criteria

1) Target Disease Exceptions

- a) Participants with active central nervous system (CNS) metastases, untreated CNS metastases, or with the CNS as the only site of disease are excluded. However, participants with controlled brain metastases will be allowed to enroll. Controlled brain metastases are defined as no radiographic progression for at least 4 weeks following radiation and/or surgical treatment (or 4 weeks of observation if no intervention is clinically indicated), off steroids for at least 2 weeks, and no new or progressive neurological signs and symptoms.
- b) Participants with carcinomatous meningitis.

2) Prohibited Treatments

- a) Cytotoxic agents, unless at least 4 weeks have elapsed from last dose of prior anticancer therapy and initiation of study treatment.
- b) Non-cytotoxic agents, unless at least 4 weeks or 5 half-lives (whichever is shorter) have elapsed from the last dose of prior anti-cancer therapy and the initiation of study treatment. If 5 half-lives is shorter than 4 weeks, agreement with the Sponsor/Medical Monitor/Study Director (or designee) is mandatory.
- c) Prior immunotherapy treatments, unless at least 4 weeks or 5 half-lives (whichever is shorter) have elapsed from the last dose of immune therapy and initiation of study treatment.
- d) Prior therapy with any agent specifically targeting T-cell co-stimulation pathways, such as anti-OX40 antibody, anti-CD137, anti-GITR antibody, and anti-CD27.
- e) Prior therapy with anti-ICOS antibody.
- f) No prior adverse reaction to tetanus toxoid-containing vaccines.
- g) Participants with known allergies to egg products, neomycin, or tetanus toxoid are also considered ineligible

3) Medical History and Concurrent Diseases

- a) Prior malignancy active within the previous 2 years except for locally curable cancers that have been apparently cured, such as basal or squamous cell skin cancer, superficial bladder cancer, or carcinoma in situ of the prostate, cervix, or breast.
- b) Prior organ allograft.
- c) Toxicity (except for alopecia) related to prior anti-cancer therapy and/or surgery, unless the toxicity is either resolved, returned to baseline or Grade 1, or deemed irreversible.
- i) Any active neuropathy Grade > 2 (NCI CTCAE v4.03²⁷).
- d) Participants with the following:
 - i) Active, known, or suspected autoimmune disease.
 - (1). Participants with well-controlled asthma and/or mild allergic rhinitis (seasonal allergies) are eligible.
 - (2). Participants with the following disease conditions are also eligible:
 - a. Vitiligo.
 - b. Type 1 diabetes mellitus.

Revised Protocol No.: 04 Date: 31-May-2019

- c. Residual hypothyroidism due to autoimmune condition only requiring hormone replacement.
- d. Euthyroid participants with a history of Grave's disease (participants with suspected autoimmune thyroid disorders must be negative for thyroglobulin and thyroid peroxidase antibodies and thyroid-stimulating Ig prior to the first dose of study treatment).
- e. Psoriasis not requiring systemic treatment, or conditions not expected to recur in the absence of an external trigger.
- e) History of life-threatening toxicity related to prior immune therapy (eg, anti-CTLA-4 or anti-PD-1/PD-L1 treatment or any other antibody or drug specifically targeting T-cell co-stimulation or immune checkpoint pathways) except those that are unlikely to re-occur with standard countermeasures (eg, hormone replacement after adrenal crisis).
- f) Interstitial lung disease that is symptomatic or that may interfere with the detection or management of suspected drug-related pulmonary toxicity.
- g) Conditions requiring systemic treatment with either corticosteroids > 10 mg daily prednisone equivalents or other immunosuppressive medications within 14 days of study treatment administration, except for adrenal replacement steroid doses \leq 10 mg daily prednisone equivalent in the absence of active autoimmune disease.
 - ii) Treatment with a short course of steroids (< 5 days) up to 7 days prior to initiating study treatment is permitted.
- h) Uncontrolled or significant cardiovascular disease including, but not limited to, any of the following:
 - i) Myocardial infarction or stroke/transient ischemic attack within the past 6 months.
 - ii) Uncontrolled angina within the past 3 months.
 - iii) Any history of clinically significant arrhythmias (such as ventricular tachycardia, ventricular fibrillation, or torsades de pointes).
 - iv) History of other clinically significant heart disease (eg, myocarditis, cardiomyopathy, congestive heart failure with New York Heart Association functional classification III to IV [Appendix 9], pericarditis, or significant pericardial effusion).
 - v) Cardiovascular disease-related requirement for daily supplemental oxygen therapy.
 - vi) QT interval corrected for heart rate using Fridericia's formula (QTcF) prolongation > 480 msec, except for right bundle branch block.
- i) History of chronic hepatitis as evidenced by the following:
 - i) Any positive test result for hepatitis B virus or hepatitis C virus indicating presence of virus, eg, hepatitis B surface antigen (Australia antigen) positive, or hepatitis C antibody positive (except if hepatitis C ribonucleic acid [RNA] negative).
- j) Evidence of active infection that requires systemic antibacterial, antiviral, or antifungal therapy ≤ 7 days prior to the first dose of study treatment (except for viral infections that are presumed to be associated with the underlying tumor type required for study entry).

k) Known history of testing positive for human immunodeficiency virus (HIV) or known acquired immunodeficiency syndrome.

Note: Testing for HIV-1 and HIV-2 must be performed at sites where mandated by local requirements.

- Any major surgery within 4 weeks of the first dose of study treatment. Participants must have recovered from the effects of a major surgery or significant traumatic injury at least 14 days before the first dose of study treatment.
 - i) Participants who have received a live / attenuated vaccine within 30 days of first treatment.
 - (1). The use of inactivated seasonal influenza vaccines (eg, Fluzone[®]) will be permitted on study without restriction.
- m) Receipt of packed red blood cells or platelet transfusion within 2 weeks of the first dose of study treatment.
- n) Any known or underlying medical or psychiatric condition and/or social reason that, in the opinion of the investigator or Sponsor, could make the administration of study treatment hazardous to the participants or could adversely affect the ability of the participant to comply with or tolerate the study.
- o) WOCBP who are pregnant or breastfeeding.

4) Allergies and Adverse Drug Reaction

- a) History of allergy to study treatment components.
- b) History of severe hypersensitivity reaction to any mAb.

5) Other Exclusion Criteria

- a) Prisoners or participants who are involuntarily incarcerated. (Note: under certain specific circumstances, and only in countries where local regulations permit, a person who has been imprisoned may be included or permitted to continue as a participant. Strict conditions apply, and BMS approval is required.)
- b) Participants who are compulsorily detained for treatment of either a psychiatric or physical (eg, infectious disease) illness.
- c) Participants with serious or uncontrolled medical disorders

Eligibility criteria for this study have been carefully considered to ensure the safety of the study participants and that the results of the study can be used. It is imperative that participants fully meet all eligibility criteria.

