5.1.1 Screening

The screening phase will last for up to 28 days and take place prior to the first administration of study treatment. During the screening phase, the participant's initial eligibility will be established, and written informed consent will be obtained. Tumor biopsies will be collected for all participants and sent for central evaluation of ICOS expression by immunohistochemistry, and all participants will receive the tetanus booster vaccine 3-7 days prior to Cycle 1 Day 1 of first administration of study treatment. Stool will be collected for microbiota composition analysis. Participants will be enrolled using the Interactive Response Technology (IRT). The screening assessments are shown in Table 2-1.

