7 TREATMENT

Study treatment is defined as any investigational treatment(s) or marketed product(s) intended to be administered to a study participant according to the study randomization or treatment allocation.

Study treatment includes IPs/investigational medicinal products (IMPs) and non-IPs/IMPs and can consist of the following:

- BMS-986226
- Nivolumab
- Ipilimumab
- Tetanus Vaccine

An IP, also known as IMP in some regions, is defined as a pharmaceutical form of an active substance or placebo being tested or used as a reference in a clinical study, including products already with a marketing authorization but used or assembled (formulated or packaged) differently from the authorized form, used for an unauthorized indication, or when used to gain further information about the authorized form.

Other medications used as support or escape medication for preventative, diagnostic, or therapeutic reasons, as components of the standard of care for a given diagnosis, may be considered as non-IPs.

Product Description / Dosage Form	Potency	IP/NonIMP	Blinded or Open Label	Packaging / Appearance	Storage Conditions (per Label)
BMS-986226-01 Solution for Injection	10 mg/mL	IP	Open	Vial	2 to 8 °C, Protect from light
Nivolumab Solution for Injection	10 mg/mL	IP	Open	Vial	2 to 8 °C, Protect from light and freezing
Ipilimumab Solution for Injection	5 mg/mL	IP	Open	Vial	2 to 8 °C, Protect from light and freezing
Tetanus vaccine	Per local ^a	IP	Open	Various packaging configuration	Refer to the label on container and/or pharmacy manual

Abbreviations: IP = investigational product

^a Tetanus vaccine (Tdap preferred, Td or equivalent after discussion with the Medical Monitor/Study Director or designee) will be obtained as local commercial product in countries if allowed by local regulations or through investigating sites standard prescribing procedures.

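### Exclusion criterion 2f is worded as an inclusion condition, so read literally it excludes participants without a prior tetanus-vaccine reaction and does not itself exclude those with one

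*Combined protocol and SAP*

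**What the plan says.** Section 6.2 is headed as the exclusion list. Under its second group, on prohibited treatments, three consecutive items read:

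- 2e: "Prior therapy with anti-ICOS antibody"
- 2f: "No prior adverse reaction to tetanus toxoid-containing vaccines"
- 2g: "Participants with known allergies to egg products, neomycin, or tetanus toxoid are also considered ineligible"

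Section 6.2, item 4a, separately excludes on "History of allergy to study treatment components". Section 7 lists tetanus vaccine as study treatment, alongside BMS-986226, nivolumab and ipilimumab. Section 5.1.1 states that "all participants will receive the tetanus booster vaccine 3-7 days prior to Cycle 1 Day 1". Table 2-1 applies this to every part and waives the booster only if one was given within 6 weeks of starting study drug.

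Eligibility is strict. Section 6 opens by ruling out exceptions, Section 9 disallows waivers, and Section 6.2 closes with "It is imperative that participants fully meet all eligibility criteria".

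**The concern.** An item in an exclusion list works by matching: a participant who fits the description is kept out. Item 2f describes the person the trial wants, so matching it gives the wrong result. The person with no history of reaction fits the description, and the person with such a history does not.

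The criterion screens for fitness to receive a vaccine that the protocol itself gives, a few days before first dosing. Because exceptions and waivers are ruled out, a site has no sanctioned way to work around the wording. A site that follows the text reaches the wrong eligibility result, and one that follows the evident intent departs from the text. On a yes/no form copied from 2f, a yes could be scored as eligible at one site and ineligible at another.

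**Working it through.** The plan states no figure on this point, so the main check is one of logic.

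**Step 1: direction of the neighbouring items.** Items 2a to 2e each name something whose presence excludes, subject to washout periods in 2a to 2c. Item 2g says outright that the people it describes are ineligible. Item 2f is the only item in the group phrased as a desired state.

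**Step 2: result for each kind of participant.**

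| Participant | 2f as written | 2f as evidently meant | Other items in 6.2 |
|---|---|---|---|
| No prior reaction, no known allergy | Excluded | Not excluded | None applies |
| Prior reaction, recorded as known tetanus toxoid or component allergy | Not excluded | Excluded | Excluded by 2g or 4a |
| Prior reaction, not recorded as allergy | Not excluded | Excluded | Only 3n, at the discretion of investigator or sponsor |

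The literal reading goes wrong in the first and third rows. In the second row 2f also gives the wrong answer, but 2g or 4a corrects it.

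**Step 3: can the opening of Section 6 rescue the wording?** Section 6 says that the criteria which follow have to be met. If that sentence governs 6.2 as well as 6.1, then 2f reads correctly as a condition to be met. On the same reading, 2e would require previous anti-ICOS treatment, which cannot be intended. Either way, at least one item in the group points in the wrong direction.

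**Step 4: is the point stated correctly elsewhere?** The inclusion criteria in Section 6.1 contain no item on reactions to tetanus vaccine. Item 2f is therefore the only specific rule for a reaction that was not recorded as an allergy.

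**Step 5: how many participants could be screened under this wording?** The inputs are approximately 234 planned participants (Section 5.2), 21 treated by 28-March-2019 (Section 3.2.2.4), and about 80 in Parts D and E (Section 5.2), which Section 5.1.2.4 says await a further protocol revision.

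234 − 21 − 80 = 133

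This is an upper figure. The 234 is approximate and allows for Parts B2 and C2, which open only if more data are needed. The 21 is a count from about two months before this version, dated 31-May-2019.

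**The case against.** The best defence is that nobody would be misled. Section 6.2 is not a pure list of disqualifying features: 3l includes a requirement to have recovered from surgery, and 3d and 3g contain permissive text. Item 2g makes the intended meaning of 2f plain. Treated numbers rose from 12, as reported with Revised Protocol 03, to 21 by the later cut-off, so enrolment was not blocked. On this view 2f is an editorial slip that touches no endpoint, analysis or sample size.

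Much of this stands. A human screener would probably read 2f as intended, and the slip has no statistical consequence. The enrolment argument is only suggestive, because the documents do not show when 2f was added. None of it makes the written rule correct, and a protocol that forbids exceptions should not depend on sites inferring the opposite of its text.

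Four stronger readings might be inferred, and the documents do not support them:

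- *That the trial admits people allergic to the vaccine.* Items 2g and 4a exclude known tetanus toxoid or component allergy whatever 2f says.
- *That almost everyone is barred.* This assumes that prior reactions are uncommon, and the documents give no rate. The inversion does not depend on one.
- *That all 234 − 21 = 213 remaining participants are affected.* That count includes the roughly 80 in Parts D and E, and being screened under a faulty line is not the same as being wrongly screened.
- *That an electronic check has been built the wrong way round or that deviations have already followed.* No eligibility form or IRT logic is available to show either.

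**Conclusion.** Item 2f is wrong as written and should be corrected. The inversion rests on the text alone and needs no assumption about reaction rates. Its safety consequence is limited to prior adverse reactions not recorded as allergy, where only the discretionary item 3n remains. The more likely cost is uneven screening between sites and eligibility deviations that a clear sentence would prevent.

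At most about 133 participants remained to be treated under this version at the cut-off. How many of them either reading would misclassify cannot be estimated. Parts D and E would inherit the wording unless the later revision corrects it. The finding assumes that 2f was meant to exclude prior reactors, which the wording of 2g supports.

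**What to change.** Reconcile 2f with its exclusion heading and with 2g by stating it in the exclusion sense, so that a prior adverse reaction to a tetanus toxoid-containing vaccine is the feature that excludes. The sponsor should decide whether a severity qualifier applies; without one, the restated item would exclude any past reaction, however mild. Check that any eligibility checklist, case report form item or IRT question scores in the same direction.

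The cost is one line in the next amendment and a check of the screening forms. Design, sample size and analysis are unchanged. The only decision of substance is the severity qualifier, because it determines who is excluded.
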